APPENDIX 3 COMMONLY USED CORTICOSTEROID EQUIVALENTS

Medication	Prednisone Dose Equivalence
Prednisone	1 mg
Cortisone	5 mg
Hydrocortisone	4 mg
Prednisolone	1 mg
Methylprednisolone	0.8 mg
Triamcinolone	0.8 mg
Budesonide	0.25 mg
Dexamethasone	0.16 mg
Bethamethasone	0.16 mg

APPENDIX 4 MEDICATION WASHOUT PERIODS

WASHOUT TIMES OF MEDICATIONS BASED ON 5 HALF-LIVES

Medication	Discontinuing Prior to Signing Consent
Abatacept (CTLA4Ig)	24 weeks
Alefacept	12 weeks
AMG 623 (blisibimod)	24 weeks
Anifrolumab	12 weeks
Atacicept (TACI-Ig)	12 weeks
Belimumab	24 weeks
Cyclophosphamide	24 weeks
Cyclosporine (except for CSA eye drops)	4 weeks for oral and 8 weeks for topical
Danazol	4 weeks
Dapsone	4 weeks
Eculizumab	12 weeks
Efalizumab	12 weeks
Epratuzumab	24 weeks
Intravenous globulin	4 weeks
Leflunomide	8 weeks (4 weeks for washout with cholestyramine)
Lenalidomide with cholestiramine	8 weeks
Lupuzor	12 weeks
Memantine	4 weeks
Natalizumab	24 weeks
Ocrelizumab	48 weeks (or 24 weeks with recovery of B cell)
Pimecrolimus	4 weeks
Plasmapheresis	24 weeks
Retinoids (oral or topical)	4 weeks
Rituximab	48 weeks (or 24 weeks with recovery of B cell)
Sirolimus	4 weeks
Tacrolimus	4 weeks
Thalidomide	8 weeks
Tocilizumab	12 weeks

APPENDIX 6 INJECTION SITE REACTION GRADING SCALE

Adverse event Injection site reaction	Grade 1	Grade 2	Grade 3	Grade 4	Grade 5
Definition: A disorder characterized by an intense adverse reaction (usually immunologic) developing at the site of an injection	Tenderness with or without associated symptoms (eg, warmth, erythema, itching)	Pain; Lipodystrophy; Edema; phlebitis	Ulceration or necrosis; Severe tissue damage; Operative intervention indicated	Life-threatening consequences; urgent intervention indicated	Death
Pain	Mild pain	Moderate pain; limiting instrumental ADL	Severe pain; limiting self-care ADL	-	-
Rash maculopapular/Erythema /Induration Definition: A disorder characterized by the presence of macules (flat) and papules (elevated). Also known as morbilliform rash, it is one of the most common cutaneous adverse events, frequently affecting the upper trunk, spreading centripetally, and associated with pruritus.	Macules/papules covering <10% BSA with or without symptoms (eg, pruritus, burning, tightness) Erythema covering <10% BSA with or without symptoms (eg, pruritus, burning, tightness)	Macules/papules covering 10% - 30% BSA with or without symptoms (eg, pruritus, burning, tightness); limiting instrumental ADL; Erythema 30% BSA with or without symptoms (eg, pruritus, burning, tightness); limiting instrumental ADL	Macules/papules covering > 30% BSA with or without associated symptoms; limiting self-care ADL Erythema covering > 30% BSA with or without associated symptoms; limiting self-care ADL	-	-

ADL = active daily living

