5.3 Treatment Period/Follow-Up Visits

The following procedures will be performed as indicated in the Schedule of Assessments (Table 1 and Table 2). See Schedule of Assessment tables for allowable windows for each visit.

- Targeted physical examination
- Vital signs (prior to PK blood draw)
- Concomitant medication documentation
- Documentation of AEs and SAEs (see Section 6.2.2.5 on SAE reporting requirements)
- PROs: CCI

- Urine pregnancy tests will be collected on WOCBP prior to study drug administration
- Injection site reaction assessments will be performed predose
- Direct Coomb's test (if indicated for hemolytic anemia)
- Spot urine for protein to creatinine ratio
- Urinalysis
- CCI [REDACTED]
- Plasma CCI [REDACTED]
- PGA, BILAG-2004 Index, SLEDAI-2K, ACR-28 joint count, and the CLASI will be completed
- SLICC/ACR Damage Index will be completed at Day 180
- C-SSRS
- ECGs prior to PK blood draw
- See [Table 1](#) and [Table 2](#) for details of PK sampling in the MAD and POC studies, respectively
- Fasting hematology and chemistry assessments
- The CD4+ count and total IgG and IgM levels
- Plasma CCI [REDACTED] & CCI [REDACTED], ADA, and whole blood for leukocyte immunophenotype
- pSTAT3 (predose [trough] samples only Phase 1b)
- nAb will be analyzed by central lab if patient is positive for ADA
- CRP
- CCI [REDACTED]

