6.2.2.6 Adverse Events of Special Interest

AEs of special interest in this study include the following:

1. Anaphylaxis and serious allergic reactions
2. Grades 2 to 5 injection site reaction, including erythema, pain, and induration (See [APPENDIX 6](#))
3. Drug Induced Liver Injury (DILI) assessed following Hy's Law
4. Malignancy (not including basal cell carcinoma or squamous cell carcinoma of skin)
5. Opportunistic infections such as disseminated histoplasmosis, cryptococcosis, disseminated herpes simplex, disseminated tuberculosis, *Aspergillus* sp., *Candida albicans*, *Coccidioides immitis*, *Cryptococcus neoformans*, *Cytomegalovirus*, *Histoplasma capsulatum*, *Isospora belli*, and *Polyomavirus JC polyomavirus*
6. Cryptosporidiasis

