6.2.7 Injection Site Reactions

Patients will be monitored for local injection site reactions as specified in the Schedule of Assessments ([Section 3.4](#)). Local injection site reactions will be assessed at 2 hours postdose at baseline, and predose for each injection after baseline. Injection site reactions should be managed according to the standard of care. Injection site reactions, Grades 2 to 5, are to be reported as AEs of special interest (see [Section 6.2.2.7.3](#)).

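### Appendix 6 cannot grade injection-site erythema, induration and pain in a way that delivers the Grade 2 to 5 adverse event of special interest the protocol defines

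*Protocol*

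**What the plan says.** Section 6.2.2.6 lists among the AESIs "Grades 2 to 5 injection site reaction, including erythema, pain, and induration" and refers to Appendix 6. Sections 6.2.2.6.2 and 6.2.7 repeat the Grade 2 to 5 rule, and Section 6.2.2.7.3 requires AESIs to be reported immediately or within 24 hours.

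Appendix 6 has three rows:

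- **General injection-site reaction.** Grade 1 is tenderness, with erythema mentioned only as a possible accompanying symptom. Grade 2 is "Pain; Lipodystrophy; Edema; phlebitis". Grade 3 includes ulceration or necrosis.
- **Pain.** Grade 1 is mild pain. Grade 2 is "Moderate pain; limiting instrumental ADL".
- **Maculopapular rash/erythema/induration.** The definition describes a generalised rash: "Also known as morbilliform rash, it is one of the most common cutaneous adverse events, frequently affecting the upper trunk". Grade 1 erythema is "Erythema covering <10% BSA with or without symptoms (eg, pruritus, burning, tightness", Grade 2 is "Erythema 30% BSA with or without symptoms (eg, pruritus, burning, tightness); limiting instrumental ADL", and Grade 3 is above 30% BSA. Induration appears in the row label only.

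On timing, Section 6.2.7 states: "Local injection site reactions will be assessed at 2 hours postdose at baseline, and predose for each injection after baseline". Section 5.3 agrees for the treatment period: "Injection site reaction assessments will be performed predose".

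**The concern.** The AESI definition names erythema and induration and sets the threshold at Grade 2. The scale it relies on measures them as a share of the whole body, which suits a widespread rash but not a reaction around one injection. If Grade 2 cannot be reached by area, or is not defined at all, the AESI count for these two signs reflects the scale and not the drug. For pain, two sites could grade the same event differently and both be following the appendix.

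Injection site reactions are a named safety endpoint in both parts (Sections 2.1 and 2.2), and repeat-dose tolerability is an objective in both. Section 3.1.2.1 says the safety review for the Phase 2 dose focused on adverse events, serious adverse events and AESIs, so the AESI classification has already entered one review.

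**Working it through.** The plan states no figure to reproduce. The check has three parts.

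**1. Can local erythema reach Grade 2 by area?** The documents give no BSA, so 1.5 to 2.2 m² (15,000 to 22,000 cm²) is an assumption. Area = fraction × BSA; diameter of the equivalent circle = 2 × √(area/π).

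- 10% BSA: 1,500 to 2,200 cm², a circle 43.7 to 52.9 cm across.
- 30% BSA (the printed Grade 2 figure for erythema): 4,500 to 6,600 cm², a circle 75.7 to 91.7 cm across.
- A 10 cm reaction: π × 10²/4 = 78.5 cm², which is 78.5/22,000 = 0.36% to 78.5/15,000 = 0.52% BSA.
- A 15 cm reaction: 176.7 cm², or 0.80% to 1.18% BSA.

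Both reactions are Grade 1 on the BSA row. The general row does not raise them, because it mentions erythema only at Grade 1.

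**2. Are the grade cells complete and consistent?**

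- *Induration:* no grade cell mentions it, so it cannot be graded from this row.
- *Erythema, 10% to below 30% BSA:* Grade 1 stops below 10%, Grade 2 is printed as 30%, and Grade 3 starts above 30%. The range between has no erythema grade. The macules/papules entry in the same Grade 2 cell reads 10% to 30%.
- *Mild pain:* Grade 1 on the pain row. The general row puts pain at Grade 2 without qualification. The same event is an AESI on one row and not on the other.

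**3. When is the site first checked after each injection?** Nominal days from dose to the next scheduled injection-site assessment, from Tables 1 and 2 (dosing on Days 0, 30, 60, 90, 120, 150 and 180):

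| Group | Dose 1 | Doses 2 to 6 | Dose 7 |
|---|---|---|---|
| Phase 1b | 2 hours, then 7 | 30 each | 7 |
| POC, PK participants | 2 hours, then 30 | 30 each | 7 |
| POC, not in PK | 2 hours, then 30 | 30 each | 30 |

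With the ±3-day windows, the 30-day gap for doses 2 to 6 runs from 30 − 6 = 24 to 30 + 6 = 36 days.

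**The case against.** Several counter-arguments have force.

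- **BSA is not the only route to Grade 2.** Pain, edema, phlebitis and lipodystrophy are Grade 2 on the general row at any size, and ulceration is Grade 3. If the semicolon before the ADL wording means 'or', erythema that limits daily activities would also qualify; the appendix does not say. This stands, and it confines the under-grading to erythema and induration without such features. Section 6.2.2.6 nevertheless names both signs as AESIs.
- **The general row also keeps erythema at Grade 1.** True, so the two rows agree on erythema. That agreement is what puts Appendix 6 at odds with an AESI definition expecting erythema at Grade 2 and above.
- **The printed 30% may be a lost lower bound.** Likely, given the parallel entry. Even at 10% a local reaction would not reach it.

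A reader might infer more than the documents support:

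- *That reactions to every dose from 2 to 7 are sought only before the next dose.* Dose 7 has no next dose. Site checks follow on Days 187 and 195 for Phase 1b and POC PK participants, and on Day 210 for everyone.
- *That these reactions will be missed.* Injection site reactions are reportable as adverse events (Section 6.2.2.6.2), collected from first dose onward by spontaneous report, examination or open question (Section 6.2.2.2). Phase 1b Day 44, 14 days after dose 2, has adverse-event collection and a targeted examination. Under-ascertainment is likely for transient reactions, not certain.
- *That the report would show a falsely clean local-tolerability profile.* The endpoint is not limited to Grade 2+, Grade 1 events still count, and Section 8.2.5.1 summarises events by severity. Procedures are the same in both blinded arms, so no differential bias is shown.
- *That a site check on POC Day 15 would cover repeat dosing.* Day 15 follows only dose 1, which already has a post-dose check.

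**Conclusion.** The point holds for the grading scale. Appendix 6 states a rule that, followed exactly, cannot produce the AESI defined in Sections 6.2.2.6, 6.2.2.6.2 and 6.2.7. Isolated local erythema stays at Grade 1: over the assumed BSA range, a 15 cm reaction covers at most about 1.2% against a first threshold of 10%. Induration cannot be graded, part of the erythema range has no grade as printed, and mild pain is or is not an AESI depending on the row used. Only the percentages rest on an assumption; the gaps and the pain conflict are in the text.

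Timing is secondary. For doses 2 to 6, and for dose 7 in POC patients outside PK, the first dedicated site check comes about 30 days after injection, so transient reactions are likely to be under-ascertained. The documents do not allow the size of that loss to be estimated.

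**What to change.** **Main change, Appendix 6.** Reconcile it with the AESI definition:

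- Grade injection-site erythema and induration on a local measure, for example greatest diameter, with cut-offs set by the sponsor and an explicit criterion for induration in each grade used.
- State which single row governs pain.
- If any percent-BSA entry is kept for generalised rash, correct the erythema gap.

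Apply the revised table to the POC part. At the interim cut-off, Cohorts 1, 2 and 3 had already reached 7, 6 and 4 doses (Section 3.1.2.1), so the report should note that MAD events were graded on the present scale and the two parts are not directly comparable on these signs.

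**Secondary change, Sections 5.3 and 6.2.7 with Tables 1 and 2.** The existing post-dose check could be repeated at later dosing visits. A 2-hour look would not catch delayed reactions, so this would only partly close the gap.

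**Cost.** One appendix table, plus a sentence and some schedule marks if the second change is taken up. The price is probably some more Grade 2 AESI reports, a grading difference between the two parts, and a short wait at up to six dosing visits.

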APPENDIX 7 PROTOCOL SUMMARY OF CHANGES

The protocol summary of changes was moved to the end of the protocol for easier readability.

Significant changes are described in the table below. Changed text is displayed for the first major occurrence only. Deleted text is presented in strikethrough format, and added text is presented in bold format.

Section	Description of Changes	Rationale
Global	Replace: Protocol Date and Version: 27 July 2018; V4.0 With: Protocol Date and Version: 23 January 2019; V5.0	Administrative
Global	Change: Changed Version number from V4.0 (Amendment 3) to V5.0 (Amendment 4) and Version date from 27 July 2018 to 23 January 2019 .	Administrative
Global	Made administrative and editorial (formatting, typographical, and grammatical) updates.	Administrative
PROTOCOL SUMMARY , Objectives and Endpoints, MAD Phase 1b, Secondary Objectives Section 2.1 , Study Objectives and Endpoints, Phase 1b Multiple Ascending Dose, Secondary Objectives	Replace: 
To characterize the PK of BOS161721 and select the optimal dose of BOS161721 based on safety, PK, and PD effects in patients with mild to moderate SLE. With: 
To characterize the PK of BOS161721 and select the optimal dose of BOS161721 based on safety, PK, and PD effects in patients with moderately to severely active SLE.	Error in the previous protocol; text updated to “moderately to severely active.”
PROTOCOL SUMMARY , Objectives and Endpoints, POC Phase 2, Safety Objectives Section 2.2 , Study Objectives and Endpoints, Phase 2 Proof of Concept,	Replace: 
To assess safety and tolerability of repeat doses of BOS161721 (20, 60, and 120 mg) administered SC in adult patients with moderately to severely active SLE on limited background standard of care treatment With: 
To assess safety and tolerability of repeat doses of BOS161721 at the chosen dose administered SC in adult patients with moderately to severely active SLE on limited background standard	Error in the previous protocol; text updated to reflect the POC study and not the 3 doses used in the MAD Phase 1b study.

Section	Description of Changes	Rationale
Safety Objectives	of care treatment	
PROTOCOL SUMMARY , Objectives and Endpoints, POC Phase 2, Exploratory Objectives	Replace: 
CCI [REDACTED] With: 
CCI [REDACTED]	CCI [REDACTED]
Section 2.2 , Study Objectives and Endpoints, Phase 2 Proof of Concept, Exploratory Objectives		
PROTOCOL SUMMARY , Study Design, Paragraph 5	Replace: 
A maximum daily dose of 30 mg/day of oral CS will be acceptable for eligibility for the study, however, daily dose must be tapered down to a maximum of 10 mg/day for at least 5 days prior to Day 0 (randomization day). One oral CS “burst” for increased SLE disease activity may occur during the study between Day 0 and Day 60. Tapering of steroids during the course of the study will be encouraged and should be evaluated at all visits. Tapering may occur after randomization except within 60 days of the primary (Day 210) and secondary (Day 120) endpoint assessments. Between Day 60 and Day 120, and between Day 150 and Day 210, oral CS doses must be held constant.
 With: 
A maximum daily dose of 30 mg/day of oral CS will be acceptable for eligibility for the study, however, daily dose must be tapered down to a maximum of 10 mg/day for at least 5 days prior to Day 0 (randomization day). One oral CS “burst” for increased SLE disease activity may occur during the study between Day 0 and Day 60. Tapering of steroids during the course of the study will be highly encouraged and should be evaluated at the protocol permitted visits (Day 0 through Day 60 and Day 120 through Day 150). Between Day 60 and Day 120, and between Day 150 and Day 210, oral CS doses must be held constant due to the endpoint evaluations occurring at Day 120 and Day 210.
	Protocol clarification; text was reworded to better explain the importance of tapering when allowed and to reiterate when it is not.
PROTOCOL SUMMARY , Main Criteria for Inclusion and Exclusion, Inclusion Criteria, criteria 9, c and 10	Replace: 
9. Women of childbearing potential (WOCBP; see Section 4.7 for full information regarding WOCBP, definition of menopause, and contraception):
 
c. Must agree to follow instructions for method(s) of contraception for the duration of treatment with study drug plus 5 half-lives of study drug BOS161721 plus 30 days (duration of ovulatory cycle) for a total of 36 weeks after treatment completion
	Protocol clarification.
Section 4.4 , Inclusion Criteria, criteria 9, c		

Section	Description of Changes	Rationale
and 10	
10. Men who are sexually active with WOCBP must agree to follow instructions for method(s) of contraception for the duration of treatment with study drug plus 5 half-lives of BOS161721 plus 90 days (duration of sperm turnover) for a total of 44 weeks after treatment completion
 
With:
 
9. Women of childbearing potential (WOCBP; see Section 4.7 for full information regarding WOCBP, definition of menopause, and contraception):
 
c. Must agree to follow instructions for method(s) of contraception for the duration of treatment with study drug plus 52 weeks
 
10. Men who are sexually active with WOCBP must agree to follow instructions for method(s) of contraception for the duration of treatment with study drug plus 52 weeks
	

PROTOCOL SUMMARY, Main Criteria for Inclusion and Exclusion, Exclusion Criteria criterion 2
	
Replace:
 
2. Other systemic autoimmune disease (eg, erosive arthritis, rheumatoid arthritis [RA], multiple sclerosis [MS], systemic scleroderma, or vasculitis not related to SLE)
 
With:
	
Protocol clarification.

Section 4.5, Exclusion Criteria, criterion 2
	
2. Other systemic autoimmune disease (eg, erosive arthritis, rheumatoid arthritis [RA], multiple sclerosis [MS], systemic sclerosis, or vasculitis not related to SLE)
	

PROTOCOL SUMMARY, Statistical Considerations, Paragraph 2
	
Add:
 
Two analyses are planned: 1) an interim analysis to select the POC dose based on the MAD data, and 2) a final analysis at study completion. Additionally, DMC safety analyses will be performed for each MAD cohort and throughout the POC to monitor patient safety as described in the DMC charter. An additional analysis may be performed for the MAD portion of the study when all MAD patients have completed the safety follow-up, or withdrawn from the study, and prior to the final analysis. Data from the POC part of the study will be excluded from this additional analysis.
	
Protocol clarification; text added to clarify that additional analysis would allow for flexibility if sponsor wanted to add an IA to review MAD only data.


Section 1.2.2.3, Clinical Studies, Paragraph 2
	
Replace:
 
PK data from the SAD study demonstrates BOS161721 has an extended $t_{1/2}$ (provisional single dose data indicates this to be approximately 42-46 days) which supports evaluation of monthly dosing.
 
With:
 
Final PK data from the SAD study demonstrates BOS161721 has a mean $t_{1/2}$ ranging from 80 to 87 days for doses of ≥ 30 mg in healthy subjects.
	
Updated to reflect that terminal elimination half-life ($t_{1/2}$) is due to a full Healthy Volunteer Single Ascending Dose dataset.

Section	Description of Changes	Rationale
Section 1.2.3 , Study Dose Selection, Paragraph 3	
Replace:
 
This POC dose decision will be based on evaluation of the PK, safety (inclusive of dose-limiting toxicity [DLT]), and tolerability data (and available PD/biomarker data) from Cohorts 1, 2 and 3 from the MAD portion (see Section 3.1.1.1).
 
With:
 
This POC dose decision will be based on evaluation of the PK, safety (inclusive of dose-limiting toxicity [DLT]), and tolerability data (and available PD/biomarker data) from Cohorts 1, 2 and 3 from the MAD portion (see Section 3.1.2.1 for the chosen POC dose and justification).
	Respective added section to be referenced.
Section 1.2.5.1 , Anaphylaxis and Serious Allergic Reactions, Paragraph 3	
Delete:
 
Based on the limited Phase 1 SAD study (BOS161721-01), anaphylaxis and serious allergic reactions in subjects who received BOS161721 was not observed.
	Updated to reflect that all of the data is now acquired and 'limited' no longer applies; there were no changes to the safety results.
Section 1.2.5.3 , Immune Complex Disease, Paragraph 2	
Delete:
 
Based on the limited Phase 1 SAD study (BOS161721-01), immune complex disease in subjects who received BOS161721 was not observed.
	Updated to reflect that all of the data is now acquired and 'limited' no longer applies; there were no changes to the safety results.
Section 1.2.5.4 , Infections, Paragraph 7	
Delete:
 
Based on the limited Phase 1 SAD study (BOS161721-01), infections in subjects who received BOS161721 was not observed.
	Updated to reflect that all of the data is now acquired and 'limited' no longer applies; there were no changes to the safety results.

Section	Description of Changes	Rationale
Section 1.2.5.5, Malignancy	Delete: Based on the limited Phase 1 SAD study (BOS161721-01), malignancy in subjects who received BOS161721 was not observed.	Updated to reflect that all of the data is now acquired and 'limited' no longer applies; there were no changes to the safety results.
Section 1.2.5.6, Hepatic Function Abnormality, Paragraph 2	Delete: Based on the limited Phase 1 SAD study (BOS161721-01), hepatic function abnormality in subjects who received BOS161721 was not observed.	Updated to reflect that all of the data is now acquired and 'limited' no longer applies; there were no changes to the safety results.
Section 1.2.5.7, Failure of Vaccination, Paragraph 2	Replace: The effect of BOS161721 was evaluated in in vivo single dose studies in Cynomolgus monkey in which the animals received vaccination to T-cell dependent KLH antigen to stimulate a TDAR. These in vivo studies demonstrated that BOS161721 significantly inhibited B-cell proliferation and IgG antibody responses to the KLH protein antigen; however, it is worth noting that BOS161721 administration did not produce any remarkable changes in anti-KLH antibody data for IgM, IgG1, IgG3, and IgG4 or anti-tetanus toxoid (TT) antibody data for IgM, IgG, IgG1, or IgE during the dosing phase in the same study. With: The effect of BOS161721 was evaluated in in vivo single dose studies in Cynomolgus monkey in which the animals received vaccination to T-cell dependent KLH antigen to stimulate a TDAR. These in vivo studies demonstrated that BOS161721 significantly inhibited B-cell proliferation and IgG antibody responses to the KLH protein antigen in a dose-dependent fashion; however, BOS161721 administration did not affect anti-tetanus toxoid antibody data for IgM, IgG, IgG1, or immunoglobulin E (IgE) during the dosing phase in the same study.	Protocol clarification; text added for specificity.
Section 3.1.2.1, BOS161721 POC Dose Selection and Justification	Replace: 3.1.2.1 BOS161721 Dose The optimal dose is chosen based on MAD Phase 1b safety, tolerability, immunogenicity, and PK and PD data. The dose will be	Added text for POC dose and justification.

Section	Description of Changes	Rationale
	
communicated by a letter to site investigators participating in the POC Phase 2 portion, and to the IRB/IEC.
	
	
With:
	
	
3.1.2.1 BOS161721 POC Dose Selection and Justification
	
	
The dose for the POC portion of the study is 120 mg administered SC monthly (a total of 7 doses). The rationale for the BOS161721-02 Phase 2 POC dose selection was based on cumulative safety, tolerability, immunogenicity, PK, and PD data available from an interim analysis (IA) performed during the MAD Phase 1b portion of the trial.
	
	
The data cut-off for this IA occurred on CCI [REDACTED] and included all 6 patients and 7 doses from Cohort 1 (20 mg), 12 patients and 6 doses from Cohort 2 (60 mg), and 12 patients and 4 doses from Cohort 3 (120 mg).
	
	
The safety analysis focused on incidence and severity of all AEs, SAEs, and pre-determined adverse events of special interest (see Section 6.2.2.6). The DMC and designated unblinded Boston Pharmaceuticals team met on CCI [REDACTED] and did not identify any untoward safety signals at any BOS161721 dose levels.
	
	
Because there were no safety, tolerability, or immunogenicity trends observed at the time of the IA, the Phase 2 POC dose selection was made based on available PK and PD data. pSTAT3 levels were assessed as the primary PD biomarker of IL-21R signaling levels. This is because IL-21R signaling, upon IL-21 binding, initially involves phosphorylation of JAK1/JAK3 which dissociate from the receptor complex, and phosphorylate STAT3 which translocates to the nucleus and drives IL-21-regulated gene expression. CCI [REDACTED]
	
	
The 120 mg dose will be communicated to site investigators participating in the POC Phase 2 portion, and to Institutional Review Boards (IRBs) and the Independent Ethics Committee (IEC).
	

Section 3.1.2.2, POC Study Design, Paragraph 2
	
Delete:
 
As in the MAD part of the study, each patient in the POC portion may receive a total of 7 SC monthly doses of study drug on Days 0, 30, 60, 90, 120, 150, and 180. Assessments will be completed according to the Schedule of Assessments (Section 3.4). Dose selection will be based on the DMC and sponsor's assessment of safety, tolerability, immunogenicity, and PK and PD data from the MAD portion of 30
	
Remove text to reduce redundancy with Section 3.1.2.1

Section Description of Changes Rationale

dosing on Day 0 as SLEDAI-2K < 6 is exclusionary.

Section 3.4, Schedule of Assessments, Table 2, Footnote

Add:

Table 2. Schedule of Assessments - Phase 2 Proof of Concept (POC)

Screen*	Enroll	Treatment Period Follow-up ^o										Safety Follow-Up ^o				
		-28 to -1 ^o	0 ^o	15 ^o (±3)	30 ^o (±3)	60 ^o (±3)	90 ^o (±3)	120 ^o (±3)	150 ^o (±3)	180 ^o (±3)	187 ^o (±3)	195 ^o (±3)	210 ^o (±3)	240 ^o (±3)	270 ^o (±3)	
Day ^o																
Visit Number ^o	1 ^o	2 ^o	3 ^o	4 ^o	5 ^o	6 ^o	7 ^o	8 ^o	9 ^o	- ^o	- ^o	10 ^o	11 ^o	12 ^o		

Footnote added for protocol clarification.

Section 3.4, Schedule of Assessments, Table 2, Footnote

Replace:

^o PK samples will only be collected at the investigational sites that will be participating in the PK portion of the study.

With:

^b PK samples will only be collected at the investigational sites that participate in the PK portion of the study. On PK only days (ie, Day 187 and Day 195 when no laboratory assessments are scheduled) samples will be collected at the investigational sites of the selected countries that participate in the PK portion of the study. Patients not participating in PK are not required to return for investigation site visits on Days 187 and 195.

Footnote added for protocol clarification. All subsequent footnotes after 'b' were re-lettered accordingly.

Section 3.4, Schedule of Assessments, Table 2, Footnote

Add:

Table 2. Schedule of Assessments - Phase 2 Proof of Concept (POC)

Screen*	Enroll	Treatment Period Follow-up ^o										Safety Follow-Up ^o				
		-28 to -1 ^o	0 ^o	15 ^o (±3)	30 ^o (±3)	60 ^o (±3)	90 ^o (±3)	120 ^o (±3)	150 ^o (±3)	180 ^o (±3)	187 ^o (±3)	195 ^o (±3)	210 ^o (±3)	240 ^o (±3)	270 ^o (±3)	
Day ^o																
Visit Number ^o	1 ^o	2 ^o	3 ^o	4 ^o	5 ^o	6 ^o	7 ^o	8 ^o	9 ^o	- ^o	- ^o	10 ^o	11 ^o	12 ^o		
EFFICACY-ASSESSMENTS ^o																
SLEDAI-2K ^o	X ^o	X ^b		X ^o	X ^o			X ^o	X ^o	X ^o						

Footnote added for protocol clarification.

ⁱ SLEDAI-2K should be done before randomization and dosing on Day 0 as SLEDAI-2K < 6 is exclusionary.

Section 3.4, Schedule of Assessments, Table 2, Predose and Postdose PK Window rows

Delete:

Screen*	Enroll	Treatment Period Follow-up ^o										Safety Follow-Up ^o				
		-28 to -1 ^o	0 ^o	15 ^o (±3)	30 ^o (±3)	60 ^o (±3)	90 ^o (±3)	120 ^o (±3)	150 ^o (±3)	180 ^o (±3)	187 ^o (±3)	195 ^o (±3)	210 ^o (±3)	240 ^o (±3)	270 ^o (±3)	
Day ^o																
Visit Number ^o	1 ^o	2 ^o	3 ^o	4 ^o	5 ^o	6 ^o	7 ^o	8 ^o	9 ^o	- ^o	- ^o	10 ^o	11 ^o	12 ^o		
PK Labs ^o																
Predose ^o		X ^o		X ^o												
Predose PK Window ^o		60m^o		a-3d^o	a-1d^o	a-2d^o	a-3d^o	a-1d^o	a-2d^o							
Postdose ^o			X ^o							X ^o	X ^o	X ^o	X ^o	X ^o		
Predose PK Window ^o				a-2d^o						a-2d^o	a-1d^o	a-2d^o	a-1d^o	a-2d^o		

Removed Predose and Postdose PK Window rows to reduce redundancy as these are the same as visit window rows. Repetitive text removed.

Section 4.4, Inclusion Criteria, criterion 7, b, item ii

Delete:

ii. "BILAG B:" Moderate Arthritis, Tendonitis or Tenosynovitis, (BILAG item number 42), defined as tendonitis/tenosynovitis, or active synovitis in ≥ 1 joint, (observed or throughout history), with some loss of functional range of movements which lead to some loss of functional range of motion as manifested by effects on instrumental ADLs such as:

Section 4.6.1,

Replace:

Revised to reduce

Section	Description of Changes	Rationale
Corticosteroid	
4.6.1 Oral Corticosteroid Dose
 
Prior to randomization, oral CSs (prednisone or prednisone equivalent), may be used in accordance with the investigator’s clinical judgment and best standard of care. See APPENDIX 3 for examples of equivalents.
 
A maximum daily dose of 30 mg/day of oral CS will be acceptable for eligibility for the study, however, the daily dose must be tapered down to a maximum of 10 mg/day for at least 5 days prior to Day 0 (randomization day).
 
After Day 0 (after initiation of study therapy), no up-titration above 10 mg/day is allowed except for up to 1 CS burst for increased disease activity.
 
Tapering of steroids during the course of the study will be encouraged and should be evaluated at all visits.
 
• Once a patient has received the first dose of study drug, prednisone (or prednisone equivalent) may be tapered down at the discretion of the investigator.
○ Tapering is allowed after randomization except within 60 days of the primary (Day 210) and secondary (Day 120) endpoint assessments. Between Day 60 and Day 120, and between Day 150 and Day 210, oral CS doses must be held constant. 
A maximum of 1 oral CS “burst” for increased SLE disease activity will be allowed during the study between Day 0 and Day 60, according to the following:
 
• An oral CS “burst” between Day 0 and Day 60; (an increase of ≤ 40 mg/day of prednisone or equivalent), which must be tapered down to a maximum of 10 mg/day within 2 weeks of initiation of the “burst”
○ Alternatively, a single intramuscular (IM) dose of methylprednisolone (40 mg or equivalent) is permitted○ The course of the oral CS “burst” is not permitted to extend beyond Day 60 
Treatment with inhalational CS therapy (eg, for asthma), or by any other route, is allowed. Other concomitant medications for SLE need to be taken at stable doses as per the inclusion criteria (Section 4.4).
 
With:
 
4.6.1 Corticosteroid
 
Prior to randomization, oral CSs (prednisone or prednisone equivalent), may be used in accordance with the investigator’s clinical judgment
	
redundancy and improve clarity. Text revised to clarify the meaning of “any other route” and added to address the use of CS for non-SLE conditions. Text regarding other medications not applicable to CS were removed.

Section	Description of Changes	Rationale
	
and best standard of care. See APPENDIX 3 for examples of equivalents.
 
A maximum daily dose of 30 mg/day of oral CS will be acceptable for eligibility for the study, however, the daily dose must be tapered down to a maximum of 10 mg/day for at least 5 days prior to Day 0 (randomization day).
 
Tapering of steroids during the course of the study will be highly encouraged and should be evaluated at the protocol permitted visits (Day 0 through Day 60 and Day 120 through Day 150). Between Day 60 and Day 120, and between Day 150 and Day 210, oral CS doses must be held constant due to the endpoint evaluations occurring at Day 120 and Day 210.
 
• Once a patient has received the first dose of study drug (after Day 0), prednisone (or prednisone equivalent) dose is highly encouraged to continue tapering down as appropriate. The investigator should evaluate the prednisone dose at each visit and make the decision, within the protocol allowed windows.
○ Exception: Between Day 60 and Day 120, and between Day 150 and Day 210 (ie, within 60 days of primary and secondary endpoint assessments), oral CS doses must be held constant. 
After Day 0 (first dose of study drug), a maximum of 1 oral CS “burst” for increased SLE disease activity will be allowed between Day 0 and Day 60, according to the following:
 
• The oral CS dose is allowed to increase to ≤ 40 mg/day of prednisone or equivalent, which must be tapered down to ≤ 10 mg/day within 2 weeks of initiation of the “burst”
○ Alternatively, a single intramuscular (IM) dose of methylprednisolone (40 mg or equivalent) is permitted○ No increase of oral CS above baseline is permitted beyond Day 60 
Treatment with inhalational CS therapy (eg, for asthma), or by any other route, but systemic administration, is allowed.
 
Treatment with intra-articular or intravenous CS is prohibited during the course of the study.
	
Section 4.7.2, Contraception, Paragraphs 1, 2, and 5	Replace: WOCBP must agree to follow instructions for method(s) of contraception for the duration of treatment with study drug plus 5 half-lives of study drug BOS161721 plus 30 days (duration of ovulatory cycle) for a total of 36 weeks after treatment completion.	Protocol clarification.

Section	Description of Changes	Rationale
	
Men who are sexually active with WOCBP must agree to follow instructions for method(s) of contraception for the duration of treatment with study drug plus 5 half-lives of study drug BOS161721 plus 90 days (duration of sperm turnover) for a total of 44 weeks after treatment completion.
 
Azoospermic men and WOCBP who are continuously not heterosexually active are exempt from contraceptive requirements. However, they must still undergo pregnancy testing.
 
With:
 
WOCBP must agree to follow instructions for method(s) of contraception for the duration of treatment with study drug plus 52 weeks, due to the mean terminal ½ life of the study drug.
 
Men who are sexually active with WOCBP must agree to follow instructions for method(s) of contraception for the duration of treatment with study drug plus 52 weeks, due to the mean terminal ½ life of the study drug.
 
Azoospermic men and WOCBP who are continuously not heterosexually active are exempt from contraceptive requirements. However, WOCBP must still undergo pregnancy testing.
	
Section 5.1, Screening	
Add:
 
 • Laboratory evaluations (non-fasting): 
 ○ FSH (postmenopausal women under age 55 years) 	Protocol clarification.
Section 6.2.2.5, Seriousness of Adverse Events	
Delete:
 
 • Is another important medical event (see below) 	Revised for clarity.
Section 6.2.2.6, Adverse Events of Special Interest	
Replace:
 
 4. Malignancy 5. Opportunistic infections such as disseminated histoplasmosis, cryptococcosis, and disseminated tuberculosis 
With:
 
 4. Malignancy (not including basal cell carcinoma or squamous cell carcinoma of skin) 5. Opportunistic infections such as disseminated histoplasmosis, cryptococcosis, disseminated herpes simplex, disseminated tuberculosis, Aspergillus sp., Candida albicans, Coccidioides immitis, Cryptococcus neoformans, Cytomegalovirus, Histoplasma capsulatum, Isospora belli, and Polyomavirus JC polyomavirus 	Text added 1) to clarify that basal cell carcinoma is not a neoplasia associated with immune suppression, but rather secondary to sun exposure and 2) to clarify specific opportunistic infections of special interest in this study.
Section 6.2.2.6.4, Malignancy,	
Add:
	Revised to align with text for

Section	Description of Changes	Rationale
Paragraph 2	
After the first dose of study drug, when there is a decision to biopsy a potentially malignant tumor, lymph node, or other tissue (with the exception of suspected basal cell/squamous cell), the investigator and/or consultant(s) should contact the sponsor clinicians or designee to discuss the issue and any decisions as soon as possible. Basal cell carcinoma or squamous cell carcinoma of skin is not considered an AE of special interest.
	
AEs of special interest.

Section 6.2.2.6.5, Special Infections
	
Replace:
 
Any diagnosis or suggested diagnosis of opportunistic infections such as disseminated histoplasmosis, cryptococcosis, shingles, disseminated herpes simplex, or disseminated tuberculosis will be recorded as AEs of special interest.
 
With:
 
Any diagnosis or suggested diagnosis of opportunistic infections such as disseminated histoplasmosis, cryptococcosis, disseminated herpes simplex, disseminated tuberculosis, Aspergillus sp., Candida albicans, Coccidioides immitis, Cryptococcus neoformans, Cytomegalovirus, Histoplasma capsulatum, Isospora belli, or Polyomavirus JC polyomavirus will be recorded as AEs of special interest.
	
Revised to align with text for AEs of special interest.

Section 8, Statistics	
Add:
 
 An additional analysis may be performed for the MAD portion of the study when all MAD patients have completed the safety follow-up or withdrawn from the study, and prior to final analysis. Data from the POC part of the study will be excluded from this additional analysis. 	
Analysis added to allow the sponsor to perform another interim evaluation of the MAD only data after all subjects complete or discontinue if wanted.

